Include a diagram that provides a quick “snapshot” of the study. For examples of study schemas, refer to the [FDA and NIH's Study Schema Examples](#) document available on the IRB website:

B. Introduction

B.1 Background and Rationale

1. *Describe the relevant prior experience and gaps in current knowledge:*
2. In the current era of growing mental health awareness, it has become clear that patients have feelings of anxiety that can negatively affect the quality of their healthcare experience. Though pharmacological interventions are widely used to treat the symptoms of anxiety, these drugs often come with a risk of serious side effects and/or dependence. Alternatively, music has been used for centuries as a medium for healing, but only recently has it become a focus of research. To date, the beneficial effects of music for pain management, anxiety, and on various hemodynamic parameters have been demonstrated in several studies. Specific selections of Mozart sonatas have helped improve patient anxiety, reduce systemic stress markers, and lower blood pressure and heart rate in patients with cancer receiving chemotherapy and in patients and in patients in the ICU. In addition, it has been shown that listening to other genres of patient-preferred music can reduce preoperative anxiety and use of music intra-operatively has been associated with decreased anxiety in patients undergoing a cesarean section. Given the unique physiologic states and medical considerations surrounding pregnant individuals and their fetuses, parturients are a patient population in which non-pharmacological techniques for anxiety reduction can be particularly beneficial.

These beneficial effects can be particularly helpful in patients with histories of substance abuse who may not wish to use pharmacological interventions for anxiety reduction, regardless of the type of medication.

1. *Describe any relevant preliminary data:*

Previous study, IRB #STUDY00001496, found preliminary results that indicated as few as 4 minutes of music listening time was sufficient to produce a 1-point reduction in anxiety on the 0-10 scale. This was found using the Mozart selections that we plan to use again for this study. We will base our starting point for music listening duration off of this preliminary data.

2. *Provide the scientific or scholarly background for, rationale for, and significance of the research based on the existing literature and how it will add to existing knowledge:*

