- Once the music play duration has lapsed, the study subject will be asked to then reassess their anxiety level on the same 1-10 scale as pre-music intervention. This reassessment will be performed at three event points: directly following completion of music duration, just prior to transport to the OR, and directly upon arrival in the OR. STAI questionnaire completion will be assessed only directly following completion of the intervention, not before transport to the OR or upon arrival in the OR. Heart rate and blood pressure measurements will be recorded at all three post-intervention assessments. After completion of the final post-music assessment, this will conclude the study subject’s participation.
- Pre- and post-music anxiety scores will be recorded and correlated to the study subjects’ assigned 3-digit codes.
- Once all 30 (or 33 maximum) subjects in each intervention group have undergone the study protocol, their pre- and post-anxiety data will be analyzed.

Please also describe the following concerning procedures:

- a. *How individuals will be screened for eligibility. Specify screening that will take place prior to informed consent and screening that will take place after informed consent:*
Patients will be screened for eligibility by the PI or Co-I and will be required to meet all inclusion criteria and none of the exclusion criteria. To do this, a brief chart review will be performed to assess age and ASA clinical status, and to ensure that daily anxiolytic medications are not taken at baseline. After informed consent, the first 0-10 anxiety rating and STAI questionnaire will be completed by the participant. If their anxiety score is rated as 0, then at that time they will be excluded from participating in the study.
- b. *Procedures being performed to monitor subjects for safety or to minimize risks:*
As stated above, the PI or Co-I will remain nearby to continually assess volume status of the music to prevent potential tympanic membrane injury.
- c. *The source records that will be used to collect data about subjects. (Submit all surveys, scripts, and data collection forms.):*
See attached data collection and anxiety-screening forms

2. *Is there a placebo control arm?*
 Yes No
3. *Describe the following concerning pregnancy testing and birth control:*
 - a. *What type of pregnancy testing and how frequently will be conducted on women of reproductive potential. If testing will not be conducted provide the reason:*

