Check to confirm that reportable new information will be reported to the IRB per the Tufts Health Sciences IRB's [Reportable New Information policy](#). If your reporting plan to the IRB differs from the IRB's policies, please describe it in detail or specify where this information is in the protocol:

I. Statistical Considerations

I.1 Study Endpoints

1. *Describe the primary and secondary study endpoints:*

Primary endpoint: determination of the 95th percentile effective dose of music duration for anxiety reduction.

Secondary endpoint: compare the 95th percentile effective dose of music duration for anxiety reduction between the Mozart and personal-preference intervention arms.

Secondary endpoint: analyze and compare pre-and post-intervention heart rate and blood pressure measurements.

Exploratory endpoint: analyze and compare anxiety ratings at the three post-intervention event-point measurements.

Exploratory endpoint: analyze and compare anxiety ratings using the 0-10 scale with the STAI questionnaire.

2. *Describe any primary or secondary safety endpoints:* N/A

I.2 Sample Size Justification Statistical Analyses

1. *Describe the statistical analyses that will be performed for this study:*

Statistical analysis to determine the ED₉₅ will be conducted using the methods described by Pace, Stylianou, and Warltier (8).

2. *Provide a sample size justification:*

The plan is to enroll up to 33 subjects per treatment group (up to 66 total), with a minimum goal of 30 per group (60 total). This is based on prior studies that suggest 20-40 study subjects are required for adequate statistical power in sequential allocation biased coin design studies, and we expect a ~10% attrition rate. A goal of 33 subjects per group will thus likely turn into an estimated sample size of 30 after attrition, which falls well within the acceptable sample size range.

I.3 Number of Subjects

1. *Specify the number of subjects to be enrolled in total across all sites:* N/A this is not a multicenter study.

2. *Specify the number of subjects to be enrolled at the Tufts site(s)¹. Subjects who sign an ICF are considered “enrolled”. For studies that have a separate screening ICF, this number is the number of subjects who sign a screening ICF:*

- a. *Specify the number of subjects expected to be enrolled at the Tufts site (i.e. sign the screening or study ICF):*

Up to 66 subjects.

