prevented via software functions in the original generation of three-digit numbers. No part of the patient's information or MRN will be used to generate the randomly generated number. Once this unique, randomly generated 3-digit number has been assigned, all coded information will utilize this unique identification number. The 3-digit number will replace the patient's MRN on coded data. The only place where the patient's MRN and their unique 3-digit identification number will coexist is on the physical key that will be kept in the PI's locked office as detailed in section G.3.1. Coded data will be stored with a Tufts CTSI REDCap account. Records will be stored for 7 years after the study is closed with the IRB, per IRB policy. The key will be immediately destroyed once the required number of participants have been recruited and the data compiled.

3. *Describe any procedures that will be used for quality control of collected data:* continual collaboration between PI and Co-I on data collection and handling.

I.5 Randomization

Will subjects be randomized?

Yes No

If Yes respond to all of the following:

1. *Describe the randomization procedures, including the ratio of subjects randomized to each study arm:*
Randomization will be performed to assign study subjects to one of the two intervention groups using “randomizer.org” or a similar online program. This will also assign subjects to a random number to help blind later analysis. Ratio of subjects should be 50/50 in each study arm. Determination of music dosage (the duration of music played for participant listening) will be done using the biased coin up-down sequential allocation algorithm, which is not random.
2. *Describe the blinding procedures:* The PI or Co-I administering the study intervention will be unable to remain blind to the study intervention given the inherent nature of the protocol. This will also be true of the participants, as the intervention treatment arms will likely be easily distinguishable. However, the participants will remain blind to their randomized intervention group until the intervention begins. Given the nature of clinical workflow surrounding cesarean sections, blinding of anxiety level assessment will also not be feasible.

J. Drugs or Devices

1. Will the research involve drugs?

Yes No

2. Will the research involve devices?

Yes No

K. Study Administration

K.1 Setting

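### Is the ED95 left undefined because the plan does not say which post-music rating, or how large a fall, counts as a response?

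*Combined protocol and SAP*

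**What the plan says.** I.1 names the "Primary endpoint: determination of the 95th percentile effective dose of music duration for anxiety reduction", and I.5 says that the choice of duration "will be done using the biased coin up-down sequential allocation algorithm, which is not random". I.2 says that the ED95 analysis "will be conducted using the methods described by" a cited methods paper.

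F.2 has anxiety rated again "directly following completion of music duration, just prior to transport to the OR, and directly upon arrival in the OR". It adds that "STAI questionnaire completion will be assessed only directly following completion of the intervention". I.1 lists, as exploratory, a plan to "analyze and compare anxiety ratings at the three post-intervention event-point measurements", and a second exploratory comparison of the 0-10 scale with the STAI.

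The only size of fall in the text is in B.1, where a previous study found about 4 minutes of music "sufficient to produce a 1-point reduction in anxiety on the 0-10 scale". B.1 then states how that finding is used: "We will base our starting point for music listening duration off of this preliminary data". Under D.2 and D.3, a participant whose baseline rating is 0 is excluded; no other baseline rating is.

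**The concern.** In an up-down design the response definition acts twice. It decides whether the next participant in the arm gets a longer, equal or shorter duration, and it defines the probability whose 95% point is estimated. Two definitions therefore give two different ED95s, in each arm and in the comparison between arms. Re-scoring at analysis repairs this only in part, because the durations tested will have clustered around the target of the rule used for stepping.

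On first reading the plan has three candidate rating times, two instruments and no stated minimum fall. The 1-point figure in B.1 is an earlier result used to choose a starting duration, and a methods paper cannot supply this trial's anxiety threshold. Two further worries follow. The last rating, on arrival in the operating room, might come too late to set the next duration. And a participant with a low baseline could not respond at any duration if the required fall exceeded that baseline.

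**Working it through.** **The plan's own figure.** I.2 plans 33 per group, to leave 30 after about 10% attrition: 33 × 0.90 = 29.7, about 30. (Dividing instead, 30 / 0.90 = 33.3, which rounds up to 34.) The figure does not depend on the response definition, so it does not bear on this point.

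**How much the definition could matter.** Assume the fall at duration d is normal with mean m(d) and SD s. Under a rule of at least k points, the ED95 is the d at which m(d) = k + 1.645s. At the 1-point ED95, P(fall ≥ 2) = Φ(1.645 − 1/s).

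For minutes, assume also m(d) = d/4, which reads the B.1 result as a mean of 1 point at 4 minutes. Then ED95 = 4(k + 1.645s).

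| s (assumed) | P(fall ≥ 2) at the 1-point ED95 | ED95, k = 1 | ED95, k = 2 |
|---|---|---|---|
| 1 | Φ(0.645) = 74% | 10.6 min | 14.6 min |
| 1.5 | Φ(0.978) = 84% | 13.9 min | 17.9 min |
| 2 | Φ(1.145) = 87% | 17.2 min | 21.2 min |

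The 4-minute gap is only the inverse of the assumed slope, so its constancy down the table shows nothing about robustness. With a logarithmic curve, m(d) = 1 + 1.5 ln(d/4), s = 1 and whole-number scoring, ED95 = 4 exp[(k − 0.5 + 1.645 − 1)/1.5]. That gives 8.6 minutes for k = 1 and 16.7 for k = 2, a gap of about 8. The minute figures are illustrations. The percentages are free of the duration curve, but they still need normal falls, a constant SD and no floor. At s = 2 the 1-point ED95 needs a mean fall of 1 + 1.645 × 2 = 4.3 points, which nobody with a baseline of 4 or less can show.

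**How open the definition really is.**

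- *Instrument.* I.1 makes the comparison of the 0-10 scale with the STAI exploratory, and eligibility turns on the 0-10 rating. That leaves the 0-10 scale as the main measure.
- *Time.* F.2 puts the first rating at the end of the music, repeats the STAI only there, and I.1 makes the comparison across the three times exploratory. The rating directly after the music is the natural one.
- *Size.* If the scale is scored in whole numbers, any reduction is a fall of at least 1. B.1 uses 1 point as its unit of effect. The only excluded baseline is 0, which is also the only whole-number score from which a 1-point fall is impossible. The eligibility rule therefore fits a 1-point response exactly.

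**Low baselines.** Under a 1-point rule every eligible participant can respond. The problem arises only if 2 or more points are required, and no section suggests that.

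**Timing.** F.1 expects enrolment to take 3-4 months, about 90 to 120 days. With up to 33 per arm, that is 90/33 = 2.7 to 120/33 = 3.6 days between participants in the same arm. If each arm is stepped separately, a wait of up to 8 hours would delay an assignment only when participants in one arm happen to cluster.

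**Scale label.** One bullet of F.2 gives the post-music scale as 1-10 but calls it the same scale as before the music. The rest of the protocol has 0-10, so this is a clerical slip.

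**The case for a change.** The strongest case for a change is that the definition above is inferred. B.1 confines the earlier 1-point result to choosing a starting duration, and having the STAI at the first rating suggests that rating without designating it. I.5 says that neither the person giving the intervention nor the anxiety assessment is blinded, and K.2 has the co-investigator carry out the protocol. An unwritten success rule in those hands leaves room for discretion, in a design where the rule steers the data. Writing it down would cost one sentence.

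Part of this stands. The text available does not state the response, a different rule would estimate a different ED95, and one explicit sentence would be tidier. The rest is weaker. The low-baseline and timing worries fade on the protocol's own eligibility rule and enrolment rate, and the shift in minutes comes from assumed curves. The discretion is also limited: once a fall of at least 1 point is the rule, the response follows from two numbers given by the participant. Finally, asking for a definition while leaving the number to the sponsor corrects no stated rule and changes no calculation.

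**Conclusion.** The response is not spelled out in the text available, but this is a gap that those running the trial can fill sensibly. The second participant in an arm cannot be given a duration until the first is scored, so a rule has to exist from the start. The protocol's sections converge on a fall of at least 1 point on the 0-10 scale directly after the music. No stated rule has been shown to give a wrong result.

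A different rule would matter: under the assumed SDs, 74% to 87% rather than 95% would meet a 2-point rule at the 1-point ED95. That measures what is at stake if another rule were used; it is not evidence that one is.

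The conclusion assumes whole-number scoring, separate stepping in each arm, one rule used throughout for both stepping and estimation, and nothing to the contrary in the study schema or data forms, which are not available here. If those set a fall of 2 or more points, the handling of low baselines would become a real question. As the documents stand, no change is needed.

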1. *Describe the criteria that define who will be excluded in the study as a numbered list:*
 1. Patient refusal.
 2. Impaired hearing.
 3. Patient is taking at least one anxiolytic medication daily at baseline.
 4. No anxiety (a score of 0, on a scale of 0-10 of pre-music exposure anxiety) after consent is given.
 5. ASA physical status rating of IV or higher. (Incapacitating disease that is a constant threat to life; a moribund patient who is not expected to live 24 hours with or without surgery)
 6. Severe medical condition(s) of the fetus or other pregnancy complications (ex: congenital heart defects, physical malformations, pre-term delivery, etc.)
2. *Describe in detail how the eligibility criteria will be assessed and satisfied (e.g., medical record review, physical examination):*
A brief medical record review, discussion with the patient, and pre-music anxiety assessment (after consent is given) will be performed.
3. *State who will determine eligibility. Note that those who are designated to determine eligibility must have appropriate training, expertise, and oversight, for example a physician PI or Co-I on a biomedical study:*
Either the PI or Co-investigator will determine final eligibility.
4. *Can study subjects participate in another research study while participating in this research study:*
 Yes No

D.3 Withdrawal of Subjects

1. *Describe anticipated circumstances under which subjects will be withdrawn from the research without their consent:*
Participants who score a 0 on their pre-music anxiety assessment will be withdrawn from the study.
2. *Describe procedures that will be followed when subjects withdraw voluntarily or are withdrawn from the research, including the possibility of partial withdrawal from study intervention with continued data collection:*
Participants who are withdrawn from the study will be provided the standard of care at Tufts Medical Center. All collected data and identifying information will be promptly destroyed.
3. *Describe any necessary safety precautions to be applied to subjects who withdraw or are withdrawn (tapering drug doses, evaluative x-ray, etc.):*
 N/A

D.4 Recruitment and Retention

D.4.1 Local Recruitment Methods

Describe the following attributes of the recruitment plan for the local Tufts site:

1. *When, where, and how potential subjects will be recruited:*
 - a. *Source of subjects (for example, patient population, local community, etc.):*

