6. *For Humanitarian Use Device (HUD) uses provide a description of the device, a summary of how you propose to use the device, including a description of any screening procedures, the HUD procedure, and any patient follow-up visits, tests or procedures* N/A

F.3 Evaluations

Will you perform any laboratory tests for this study?

Yes No

F.4 Collection, Storage, and Use of Human Biospecimens for Unspecified Future Research (formerly referred to as “Tissue Banking”)

Will biospecimens be collected and stored for unspecified future research?

Yes No

G. Ethics and Protection of Human Subjects

G.1 Informed Consent Process

Will subjects be required to provide informed consent?

Yes No

If Yes, respond to all of the following:

1. *Where the consent process will take place (e.g. a private clinic room):*
The informed consent will be taken in-person in the pre-op area in a private room.
2. *Anticipated amount of time a potential subject will have to make a decision about participation in the study:*
The patient is anticipated to decide within roughly 15 minutes. However, this is not a cutoff and it will be ensured that patients will not be coerced and will be given ample time to think about enrollment.
3. *Processes to ensure ongoing consent throughout the study:*
The researcher will be present for the entirety of the study intervention and will be able to stop the intervention at any point if the patient wishes to discontinue their involvement. Patients will also be informed that they are able to withdraw from the study at any time.
4. *Role of each research team member involved in the informed consent process (Please note, in general, for studies designated by the IRB as greater than minimal risk, a physician PI or Co-I must perform the informed consent process with subjects. A study coordinator/clinical research associate may not consent subjects. A study coordinator/clinical research associate may assist with this process; however, the PI or Co-I should be present to discuss the study with the subject and answer questions, and the PI or Co-I should sign the ICF documenting that s/he has performed the informed consent process with the subject and the subject understands the study.):*
Either the PI or Co-I will perform the consent process.
5. *Check to confirm you will follow “[SOP: Informed Consent Process for Research \(HRP-090\)](#)”.*

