- b. *Estimate the number of subjects needed to complete the study at the Tufts site:* 60 subjects

- c. *Provide the rationale for enrolling this number of subjects at the Tufts site:*

As mentioned above, previous sequential allocation biased coin design studies suggest that 20-40 subjects are required for adequate statistical power.

- d. *If a large number of withdrawals and/or dropouts is expected, explain why:*

Withdrawal/dropout rate is expected to be roughly 10%.

I.4 Data Management

1. *Describe the data analysis plan, including descriptions of the data:*

Data collection forms and an excel spreadsheet with all the analyzed data will be stored during the study period in the PI's private locked office and/or cloud account, where access is exclusive to the research team.

2. *Describe the steps that will be taken to secure the data (e.g., training, authorization of access, password protection, encryption, physical controls, certificates of confidentiality, and separation of identifiers and data) during storage, use, and transmission:*

As mentioned above, physical data will remain in a locked private office to which access is restricted to research team members only. To separate and distinguish ICFs between this study and the previous, similar study (IRB STUDY #00001496), the physical forms will be kept in a folder/binder of a different color with clear labels. All electronic data will be held in a password protected, encrypted account within Tufts CTSI REDCap. Data will be coded. Each participant will be assigned a unique randomly generated three-digit number that will be linked with their medical record number on the key. Duplicates will be

¹ ¹ If Tufts IRB is requested to be the Single IRB of Record for external sites (as per section **Error! Reference source not found.**), include all sites in these enrollment numbers.

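### Read to cover voluntary withdrawal, the D.3 destruction rule erases post-music records on which the ED95 and the dose sequence depend

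*Combined protocol and SAP*

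**What the plan says.** **Attrition.** I.2 item 2 plans up to 33 participants per group and states "A goal of 33 subjects per group will thus likely turn into an estimated sample size of 30 after attrition". I.3 item 2d repeats the rate as a single figure: "Withdrawal/dropout rate is expected to be roughly 10" per cent. Neither place says what kinds of loss it contains. I.3 counts a participant as enrolled once she signs the consent form.

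**Withdrawal.** D.3 item 1 names one circumstance for removal without consent: "Participants who score a 0 on their pre-music anxiety assessment will be withdrawn from the study". The prompt of D.3 item 2 is wider. It asks what happens "when subjects withdraw voluntarily or are withdrawn from the research, including the possibility of partial withdrawal from study intervention with continued data collection". The answer gives standard care to participants who are withdrawn and adds: "All collected data and identifying information will be promptly destroyed". It draws no line between leaving before the music and leaving after it.

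**Ways to leave after music starts.** G.1 item 3 says the researcher "will be able to stop the intervention at any point if the patient wishes to discontinue their involvement". F.2 asks for the anxiety score at three points: "directly following completion of music duration, just prior to transport to the OR, and directly upon arrival in the OR". Participation ends only after the last of these.

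**Dose sequence.** Under I.5 item 1, the choice of music duration "will be done using the biased coin up-down sequential allocation algorithm". The primary endpoint in I.1 is the ED95. I.2 item 1 gives the analysis method by citation only.

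**The concern.** In an up-down design a participant who has started music is more than one unit of sample size. She has used a duration, and her result, or its absence, must be dealt with before the next duration is set. If she gives the immediate score and withdraws later, that score may already have steered the sequence. Destroying it then leaves a path of durations that the remaining data cannot explain, and takes a known response out of the analysis.

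An ED95 is sensitive to this because non-responses are the scarcer kind of result near the target and carry much of the information. If participants who are not helped are more likely to leave, the erased records are mostly non-responses and the estimated duration is too short. Once the records are gone, nobody can check whether this happened, or whether it differed between the Mozart and personal-preference arms.

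D.3 can also be read narrowly, as covering score-0 removals only. The plan then has no rule at all for voluntary withdrawal.

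**Working it through.** **1. The plan's own figure.** 33 × 0.90 = 29.7 per group and 66 × 0.90 = 59.4 in total, which agree with 30 and 60. The loss from 33 to 30 is 3/33 = 9.1%. There is no error here.

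**2. Three kinds of loss compared.**

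| Loss | Duration used? | Response known? | Effect of erasing the record |
|---|---|---|---|
| Score 0 before music (D.3 item 1) | No | No | Smaller number only; no effect on the dose-response data |
| Stops the music early (G.1 item 3) | Yes | No | Duration and count lost; an ED95 among all starters cannot be calculated |
| Scored after music, leaves before OR arrival (F.2) | Yes | Yes | A known response is lost, and it may have set the next duration |

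I say *may* because the plan does not state which of the three post-music scores feeds the algorithm. The immediate one is the natural reading. F.2 puts the music at 1 to 30 minutes and average participation at 3 to 4 hours, so there can be time to withdraw after that score.

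**3. Direction and size without a dose-response curve.** Let *p* be the true response probability at a duration and *f* the fraction of non-responses erased. The response seen in the remaining records is p / [p + (1 − p)(1 − f)]. Setting this to 0.95 and solving gives p = 0.95(1 − f) / [0.05 + 0.95(1 − f)].

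- f = 0: p = 0.950.
- f = 0.25: 0.7125 / 0.7625 = 0.934.
- f = 0.50: 0.475 / 0.525 = 0.905.

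With a quarter of non-responses erased, the apparent ED95 is really about an ED93.

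**4. Size in minutes (simulation).**

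- From the documents: 33 starters per arm, start at 4 min (B.1), range 1 to 30 min (F.2).
- Assumed, not in the documents: steps of 1, 2 or 3 min; log-logistic curve with slope 3; true ED95 of 8, 12 or 20 min; step-down probability after a response of 0.05/0.95 = 0.0526; isotonic regression with linear interpolation.
- Non-responses without any withdrawal average about 3 to 11 per arm, because the sequence climbs through short durations first.
- Erasing a quarter of them after they have set the next duration (about 1 to 3 records per arm) lowers the median estimated ED95 by roughly 0.2 to 0.9 min over the nine settings.
- If the erased participant is also skipped in the sequence, so that her duration is repeated, the shift can be larger. With an assumed ED50 of 5 min, ED95 of 15 min and 2-min steps, the median falls from 12.6 to 11.3 min, a drop of 1.3 min, with 1.7 records lost on average.
- For scale, the interquartile width of the estimate with no withdrawals is about 1.3 to 4.5 min.

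**5. Withdrawal unrelated to response.** In the same nine settings, skipping such participants moves the median by about 0.7 min or less, and usually by 0.3 min or less.

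**The case against.** The other side has four good arguments.

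- **D.3 is ambiguous.** Its answer speaks of participants who are withdrawn, which echoes the score-0 rule in item 1. It may never have been meant for voluntary withdrawal. This stands, so the bias is conditional on the wider reading. The prompt does name voluntary and partial withdrawal, however, and no other passage supplies a rule for them.
- **The harmful case may be rare.** A known non-response is lost only if a participant is scored and then leaves before OR arrival. A participant who stops during the music has no post-music score to destroy. The plan gives no frequency for either. This stands too.
- **Random withdrawal does little damage.** Correct, as step 5 shows. But after destruction nobody can tell whether withdrawal was related to response.
- **Deletion may be a deliberate privacy choice.** That is legitimate, and the consent wording is not available here to check. The fix therefore keeps deletion on request.

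Three stronger readings are tempting, and the documents do not support them.

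- A reader might infer that the 10% is made up of post-music withdrawals. The plan never divides it, and all of it could be score-0 removals.
- A reader might set the 3 planned losses per arm against 30 × 0.05 = 1.5 expected non-responses. That 1.5 assumes all 30 participants sit at the ED95, which an up-down sequence does not do; about 3 to 11 is realistic.
- A reader might count unscored starters as non-responses and take the resulting rise in the simulated ED95 (0.1 to 6.3 min at 3% to 10% withdrawal) as damage. That is the difference between two ways of counting, completers or starters. It is not a bias caused by D.3.

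**Conclusion.** The concern holds as a minor point about data handling. The sample-size arithmetic is not at fault. Read to cover voluntary withdrawal, D.3 item 2 can erase immediate post-music scores that belong in the ED95 analysis and may have set later durations. Read narrowly, it leaves voluntary withdrawal without a rule.

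The bias is downward if the erased records are more often non-responses: roughly 0.2 to 0.9 min in the median when a quarter of scored non-responses are erased, under the assumptions in step 4. This is modest beside the sampling spread of the estimate. It is close to nil if withdrawal is unrelated to response, and absent if every loss is a score-0 removal. The documents do not show which of these will occur, nor that withdrawal will differ between arms. The reason to act is that destroyed records cannot be recovered once the question arises.

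**What to change.** - In D.3 item 2, limit routine destruction to score-0 removals before music.
- For anyone who has started music, use the partial-withdrawal option that the form already offers. Keep the coded arm, assigned duration and any score already given, unless she asks for deletion.
- In I.2, state that every immediate post-music score enters the ED95 analysis, whatever happens afterwards.
- For participants who start music but give no score, report the count by arm. Give the ED95 once with them skipped and once with them counted as non-responses.

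The cost is matching consent wording, less complete deletion on withdrawal, and one sensitivity analysis. It needs no added participants and no new measurements. The change has to be made before the first withdrawal.
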